#### 3.5 Test Procedure

The observer will provide the subject the MGC Health COVID-19 & Flu A+B Home Multi Test and the QRI. The lot number and expiration date of the kit will be recorded. The observer will ask the subject to conduct the test. The subject will be expected to collect the sample, conduct the test, read and interpret the test result.

The observer will complete an observation form that will assess how well the subject followed the QRI to perform the critical steps for the test and interpret the test result.

The critical steps that each subject should perform accurately are as follows:

- Swab each nostril, rotating swab against nostril at least 5 times.
- Rotate the nasal swab in the sample collection tube liquid at least 5 times.
- Lift the swab out of the liquid in the collection tube and squeeze the tube against the swab tip 3 times.
- Squeeze the sample collection tube while removing the nasal swab.
- Press the nozzle lid firmly onto the sample collection tube.
- Transfer 3 drops from the sample collection tube into the sample well of test cassette.
- Do not move or lift the test cassette.
- Read the results between 15 and 20 minutes.

The subjects will interpret the test result and the observer will assess whether they agree or do not agree with the reading of the result. If they do not agree, they will provide the reason.

The observer will label each cartridge with the subject ID, protocol number, and date and will take a photograph of each test cartridge immediately after the subject has interpreted the result. Each photograph will be saved as an image titled with the subject's ID number.

After completion of the test process, the subject will complete a questionnaire on the clarity of the instructions provided, ease of performing the test, and ease of reading and interpreting their results.

The subjects will then be presented with 10 sample images of test results (1 negative, 7 positive, and 2 invalid) to confirm their ability to use the QRI to read and interpret all possible test results. The provided images will be as follows:

Image 1 - invalid test (no lines);

Image 2 – positive Flu A

Image 3 – positive COVID-19, Flu A, and Flu B

Image 4 – invalid test (Flu A line, no C line)

Image 5 – positive Flu B

Image 6 – positive Flu A, and Flu B

Image 7 - negative

Image 8 – positive COVID-19 and Flu A

Image 9 - positive COVID-19 and Flu B

Image 10 – positive COVID-19

The observer will record the subject's interpretation of the sample test results in the CRF.

Participation in the study should be completed in under one hour.

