#### 1.9 Study Design

This is an open label observational study to evaluate the usability of the MGC Health COVID-19 & Flu A+B Home Multi Test.

Each subject will be provided a MGC Health COVID-19 & Flu A+B Home Multi Test and asked to conduct the test on themselves or another subject using the Quick Reference Instructions (QRI) for the MGC Health COVID-19 & Flu A+B Home Multi Test while being monitored by an observer.

A member of the clinical study staff will observe the subject while they are conducting the test. The observer will note the completion and/or correct performance of critical steps which, if not performed correctly, could lead to an inaccurate test result.

The observer will note whether or not they agree with the subject's interpretation of the test results. A photograph of the test cartridge will be taken showing the results.

Subjects will be asked to provide their perspective on the use of the test at the end of the testing process.

In addition, a set of illustrations of test results will be provided to each subject for interpretation. Results of the testing will be used to determine whether further refinement of the QRI may be needed. The results of the testing will not be used for patient management or treatment decisions.

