# 7 STATISTICAL CONSIDERATIONS

Except where otherwise specified, the following general principles apply to the planned statistical analyses. All statistical analysis will be conducted using a current version 9.4 (or later) of SAS (SAS Institute Inc., Cary, NC), Excel version 2010 or later, or other widely accepted statistical or graphical software as required. Categorical variables (e.g., sex) will be summarized with frequency counts and percentages.

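### The observer's check of how users read their own cassette is collected, but none of the three validity criteria in section 7.1 uses it

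*Combined protocol and SAP*

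**What the plan says.** The Study Synopsis lists two primary endpoints: usability of the QRI as evaluated by the observer, and usability of the kit as evaluated by the subject.

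Section 3.5 describes the observer's form. It is to "assess how well the subject followed the QRI to perform the critical steps for the test and interpret the test result", so it has two parts: carrying out the steps, and interpreting the result. On the second part, "the observer will assess whether they agree or do not agree with the reading of the result", and a reason is given for disagreement. Section 1.9 plans the same entry: "The observer will note whether or not they agree with the subject's interpretation of the test results". The observer will also "take a photograph of each test cartridge immediately after the subject has interpreted the result".

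Section 3.5 lists eight critical steps. The only one about reading is "Read the results between 15 and 20 minutes". Each user is then shown ten sample images "to confirm their ability to use the QRI to read and interpret all possible test results".

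Section 7.1 counts usability as valid on three criteria: a mean questionnaire score of 3 or less, 80% of critical steps correct by the observer's assessment, and 80% of sample-image interpretations correct. It adds that questionnaires and observer notes may lead to changes in the QRI and to further testing. Section 7 gives a general rule for summaries: "Categorical variables (e.g., sex) will be summarized with frequency counts and percentages".

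**The concern.** Reading and interpreting one's own cassette is part of the task that section 3.5 sets each user, and the observer records whether the reading was right. The decision rule then sets that record aside. If section 7.1 is followed exactly, usability can be declared valid whatever the observer recorded about users' readings of their own cassettes. A reader of the report could see the disagreements, but how much weight to give them would be settled after the data are known. For a home test the practical question is whether a lay user ends with the right answer from the cassette they ran, and the stated rule does not ask it.

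**Working it through.** **Inputs**

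- Users: at least 15 testing themselves and 15 testing a child (Synopsis, sample size). 15 + 15 = 30, which reproduces the planned minimum. No power or precision basis is given.
- Critical steps: 8 per user (section 3.5).
- Sample images: 1 negative + 7 positive + 2 invalid = 10 per user (section 3.5).
- Thresholds: 80% for steps and 80% for images (section 7.1).
- Assumptions, not in the documents: steps and images are pooled over users; an 80% cut-off is borrowed for own-cassette agreement; the true agreement rates used below.

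**Step 1: which criterion uses which record**

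| Record | Used in section 7.1? |
|---|---|
| Eight critical steps, including when the result is read | Yes, criterion 2 |
| Ten sample images | Yes, criterion 3 |
| Questionnaire, including items 10 and 11 on reading and interpreting | Yes, criterion 1, but as self-rated ease |
| Observer agrees or disagrees with the own-cassette reading | No |

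**Step 2: effect on the verdict.** With 30 users and pooling, criterion 2 scores 8 × 30 = 240 steps (pass at 0.8 × 240 = 192) and criterion 3 scores 10 × 30 = 300 images (pass at 0.8 × 300 = 240). Let *d* be the number of own-cassette readings with which the observer disagrees, from 0 to 30. None of the three criteria contains *d*. For given steps, images and questionnaire scores, *d* = 0 and *d* = 30 give the same verdict.

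**Step 3: adding the reading as a ninth pooled step would not help.** With all 30 readings wrong and all 240 other steps right, the score is 240 / (240 + 30) = 240/270 = 88.9%, still above 80%.

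**Step 4: what a separate 80% criterion would do at exactly 30 users.** The pass count is 0.8 × 30 = 24. The exact (Clopper-Pearson) 95% interval takes its lower limit from the 0.025 quantile of Beta(24, 7) and its upper limit from the 0.975 quantile of Beta(25, 6): 61.4% to 92.3%. The chance of passing is P(X ≥ 24) for X binomial with n = 30:

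| Assumed true agreement | Chance of passing | Chance of failing |
|---|---|---|
| 60% | 0.017 | 0.983 |
| 70% | 0.160 | 0.840 |
| 80% | 0.607 | 0.393 |
| 90% | 0.974 | 0.026 |

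**Step 5: limits of that criterion.** It tolerates 30 − 24 = 6 misreadings. The mix of results is not controlled, so with 6 or fewer positive cassettes it could be met with every positive misread. Within one user group, 12/15 has an exact 95% interval of 51.9% to 95.7%, which suits description only.

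**The case against.** The strongest reply is that scoring interpretation on images is a sound design choice. The images have known answers and show every user all seven positive patterns, a negative and two invalid results. Own cassettes come in an uncontrolled mix, with no reference except the observer's view. This stands as a reason to keep criterion 3. It does not explain why the other measurement, planned in both 1.9 and 3.5, has no place in the decision.

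A second reply is that misreading is already handled. Section 7 would give counts and percentages of agreement by default, reasons for disagreement are recorded, cassettes are photographed, and section 1.9 says: "Results of the testing will be used to determine whether further refinement of the QRI may be needed". This stands as far as visibility goes. None of it is linked to the validity verdict.

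A third reply is that the endpoint does not name own-cassette reading. That is correct. The link is an inference from joining the Synopsis to the description of the form in 3.5. The form itself is not reproduced, so it may already have a field for the observer's own reading.

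Two stronger readings are tempting. One is that the plan sets no limit on misreading at all; criterion 3 is such a limit, for images. The other is that users are likely to misread their cassettes and still pass; the documents give no basis for a misreading rate. Likewise, the text does not require the observer to read before knowing the user's answer, so agreement could be inflated, but by an unknown amount and without effect on the present rule.

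**Conclusion.** The point holds in this form: the validity rule omits a measurement that the protocol collects as part of the observer's evaluation, and the verdict does not change between 0 and 30 disagreements out of 30. That follows from the text and does not depend on the assumed agreement rates or on pooling. It does rest on reading the form described in 3.5 as the observer evaluation meant in the Synopsis.

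The weight is moderate. The data are already planned and misreading would be visible, so this is a gap in the decision rule and not a failure of data collection. A hard 80% cut-off is debatable, given the wide interval at 30 users and the uncontrolled mix of results. Bringing agreement into the decision in a pre-stated way is the necessary part; a fourth threshold is the sponsor's choice.

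**What to change.** **Section 3.5.** The user writes down the result first. The observer then records the control line and the three test lines before seeing that answer, and takes the planned photograph at the same time as the record for checking. The observer does not approach the cassette before the user has written, so the timing step is not prompted. Agreement is derived from the two entries. State in advance how a conflict between the photograph and the observer's entry is settled.

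**Section 7.1.** Report beside the three criteria, as part of the validity decision:

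- the number of users whose reading of their first cassette matched the observer's reading, out of all users who ran the test, with no recorded result counted as not matching;
- an exact 95% confidence interval;
- a breakdown by observed result (negative, positive, invalid) and by user group (self-testing, testing a child), both descriptive.

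Flag readings taken outside 15 to 20 minutes: a match there shows agreement but not a correct result.

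**Optional fourth criterion.** If a pass/fail rule is wanted, keep it separate from the critical steps and require at least 80% matching. With exactly 30 users the denominator is 30 and the pass count is at least 24. The breakdown by observed result must accompany it, for the reason in Step 5 of the working.

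**Cost.** One user sheet and one extra field on the observer's form, with the same observer, visit, photograph and sample size. If the criterion is adopted, it would fail about 3% of the time at an assumed true agreement of 90%, and about 39% at 80%.

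### The observer judges the user's own-cassette result with the user's reading already known and no set time for the check, so the agreement item is open to bias towards agreement

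*Combined protocol and SAP*

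**What the plan says.** Protocol section 3.5 (Test Procedure) sets out how the subject's own result is judged. The subject interprets it, and "the observer will assess whether they agree or do not agree with the reading of the result". It adds: "If they do not agree, they will provide the reason". Section 1.9 (Study Design) states the same rule: "The observer will note whether or not they agree with the subject's interpretation of the test results". The study is open label. Nothing asks the observer to record a reading of their own first, or to look at the cassette at a set time.

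For the photograph, section 3.5 says the observer "will take a photograph of each test cartridge immediately after the subject has interpreted the result". The cartridge label is to carry the subject ID, the protocol number and the date. The image file is titled with the subject ID. No clock time is called for in either place, and no planned use of the photograph is described.

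The last of the eight critical steps in section 3.5 is: "Read the results between 15 and 20 minutes". The observer scores these steps. Section 1.9 says: "The observer will note the completion and/or correct performance of critical steps which, if not performed correctly, could lead to an inaccurate test result".

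The synopsis makes observer evaluation of the QRI the first primary endpoint, and section 3.5 has the observation form cover interpretation of the result as well as the steps. Section 1.9 says the results will inform whether the QRI needs refining. Section 7.1 has three acceptance criteria: the questionnaire mean, 80% of critical steps correct, and 80% of sample-image interpretations correct.

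**The concern.** The reference for the subject's reading is not independent of that reading, in two ways.

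- **Known answer.** The observer is asked whether they agree with an answer already in front of them. Where a line is faint, a known answer can pull the second judgement towards it. Only disagreement needs a stated reason, so agreement is also the lighter entry to make.
- **Shared moment.** The photograph follows the subject's reading, and the order of events implies that the observer's look does too. If the subject reads early, both people may correctly see a cassette whose lines have not finished developing. The record says they agree, and the photograph bears this out.

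This is the study's only measure of a lay user reading a real cassette that they ran themselves. The ten sample images have answers fixed in advance and do not test when to read. Inflated agreement could hide a weakness in the QRI that the study is meant to find.

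**Working it through.** The documents give no target, expected value or precision for own-result agreement, so there is no figure to reproduce. The check is to see what the procedure would record, and then to illustrate size.

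**Inputs from the protocol.** At least 30 completed subjects (synopsis); 8 critical steps, one of them read time (3.5); an 80% rule for steps (7.1, pooling unit not stated).

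**1. What would be recorded.**

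- In window, lines read correctly: agree, and the timing step is correct. The record is right.
- In window, lines misread: disagree with a reason if the observer sees the error; agree if the observer is led by the known answer. This is where the bias can enter.
- Out of window, displayed lines read correctly: agree, and the timing step should be scored as failed. Agreement is true of what was on the cassette, but does not show what it would have displayed at 15 to 20 minutes.
- Out of window, lines misread: both problems apply.

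**2. How many records could lack an in-window reference.** The documents give no out-of-window rate. Assuming 10% to 30%: 0.10 × 30 = 3, and 0.30 × 30 = 9.

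**3. How far a known answer could inflate agreement.** Let p be the true share of correct own readings and w the share of wrong readings recorded as agreement. Both are assumed, and correct readings are taken never to be marked as disagreement. Then

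recorded agreement = p + (1 − p) × w.

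With p = 0.80:

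- w = 0: 0.80 + 0.20 × 0 = 0.80
- w = 0.25: 0.80 + 0.20 × 0.25 = 0.85
- w = 0.50: 0.80 + 0.20 × 0.50 = 0.90
- w = 1: 0.80 + 0.20 × 1 = 1.00

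The binomial chance of at least 27 of 30 recorded agreements (27/30 = 90%, chosen only for illustration) is 0.12 at w = 0, 0.32 at w = 0.25 and 0.65 at w = 0.50.

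**4. How much the timing step protects.** If the 80% rule is pooled over subjects and steps, there are 30 × 8 = 240 steps; 0.80 × 240 = 192 must be correct, so 48 errors are allowed. If every subject read outside the window and did everything else correctly, the score would be 30 × 7 = 210, and 210/240 = 87.5%, a pass. The error is recorded, but a pooled rule need not react to it.

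**The case against.** The strongest reply is that timing and comprehension are different questions and the protocol records them separately. Someone who reads at 8 minutes should be scored as failing the read-time step, on the same observation form. For comprehension, the proper reference is the cassette as the subject saw it, so an immediate photograph is right. The objective is usability, and no comparator assay is planned. The observer must look at the lines in order to disagree and give a reason, and the photograph allows a misread line to be checked later. No acceptance criterion uses own-result agreement.

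Most of this stands, and it rules out three stronger readings that a reader might infer:

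- *That early or late readings disappear as correct results.* They do not, because read time is a scored step. How a pooled 80% rule treats that step is a question about section 7.1.
- *That the pass or fail decision is biased.* Section 7.1 judges interpretation on the sample images, whose answers do not depend on the observer or on read time.
- *That every error is recorded as agreement, or that bias always runs that way.* Disagreement is provided for, and the documents do not show the direction or size of any bias. Agreement is the expected direction, no more. The moment of the observer's look is also implied by the sequence, not written down.

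The reply does not remove the lack of independence. A later check of the photograph is possible but not planned, and an out-of-window photograph cannot by itself show the in-window result. A careless remedy would also do harm: an observer who approached the cassette near 15 minutes could cue the subject to read, and section 3.1 requires that the subject's activities are not interfered with.

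**Conclusion.** The point holds in a limited form. Own-result agreement is an unblinded judgement made with the subject's answer known, and no independent reading is required. It is open to bias towards agreement. For readings outside the window it shows only that both people saw the same lines. What is affected is the evidence behind primary endpoint 1 and the decision on refining the QRI, not the section 7.1 criteria directly.

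The size cannot be established from the documents. The 3 to 9 of 30 records rest on an assumed 10% to 30% out-of-window rate. The rise in recorded agreement from 0.80 to 0.85 or 0.90 rests on assumed values of p and w. The observation form is not in the documents; if it already asks for a prior observer reading and a clock time, much of the point is met. This is an inexpensive improvement worth making before enrolment, because an in-window reference not captured at the visit cannot be recovered afterwards.

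**What to change.** Amend section 3.5, with matching words in 1.9 and on the observation form:

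1. The subject writes down their result without saying it aloud.
2. Once the subject has finished, so that read time is not cued, the observer records their own reading of C, COVID-19, Flu A and Flu B with the clock time, before seeing the subject's answer.
3. Agreement is derived by comparing the two records.
4. The time of each photograph is recorded. If the subject read before 15 minutes, a second photograph of the same cassette is taken at 15 to 20 minutes.
5. Agreement is reported separately for readings inside and outside the window. Late readings are shown as out of window and not counted as disagreements, since the timing step already records that error.

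For late readers no in-window photograph can be required without risking a cue, so their agreement stays a statement about the lines as seen.

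The cost is a few form fields, a short wait for early readers within the same visit, and possibly a lower agreement rate. The change affects measurement only, not how the test is run.

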# **4 PREMATURE STUDY TERMINATION OR SUSPENSION**

#### 4.1 Termination or Suspension

This study may be suspended or prematurely terminated by the sponsor or the investigator immediately upon notice for any cause. Written notification via email or post, documenting the reason for study suspension or termination, will be provided by the suspending, or terminating party. If the study is prematurely terminated or suspended, the principal investigator will promptly inform the IRB and will provide the reason(s) for suspension or termination.

#### 4.2 Circumstances Warranting Termination or Suspension

Circumstances that may warrant termination include, but are not limited to:

- 1. Insufficient adherence to protocol requirements.
- 2. Data that are not sufficiently complete and/or evaluable.

3. Determination of futility

# **5 SAFETY CONSIDERATIONS**

#### 5.1 Safety Warnings and Precautions

All samples should be handled as potentially infectious. Use an appropriate disinfectant for decontamination. Store and dispose of these materials and their containers in accordance with local regulations and guidelines.

#### 5.2 Definition of Adverse Events

An Adverse Event (AE) is any untoward medical event that occurs to the subject during the course of a study (with onset after the first study-specific procedure), whether or not that event is considered study-related.

An adverse event may be mild, moderate, or severe and is usually unexpected.

All adverse events observed by the principal investigator or reported by the subject must be reported to the sponsor within 24 hours. To report an adverse event, the principal investigator will complete an adverse event form or relevant form located in the CRF.

Adverse events will be considered study-related if the event follows a reasonable temporal sequence from a study related procedure and could readily have been produced by that study procedure. For the purpose of this study, only the collection of nasal nares swab is considered to be the study procedure.

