#### 6.2 Responsibility of Investigator

The principal investigator is responsible for the proper conduct of the study at their site(s). The investigator will ensure that the study is conducted in compliance with the protocol, the Clinical Study Agreement, and applicable regulations in 45 CFR 46, and any other applicable regulatory requirements. These requirements include:

- Obtaining IRB approval for the study and related documents before study initiation enrolling subjects.
- Obtaining informed consent from each subject in accordance with 21 CFR Part 50, as applicable.
- Protecting the rights, safety, and welfare of subjects under their care.
- Reporting adverse events.
- Coordinating and providing reasonable medical care to subjects for an adverse event related to study participation.
- Reporting protocol deviations to the sponsor and IRB per IRB requirements.
- Maintaining traceability and secured storage of all test kits and study samples.
- Ensuring confidentiality of all study documents, procedures, and study samples.

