# **11 SUBJECT QUESTIONNAIRE**

The following questionnaire will be presented to subjects after completion of the MGC Health COVID-19 & Flu A+B Home Multi Test.

Subject Questions

- 1. Overall, how easy or difficult was it to understand the instructions to conduct the test?
  - 1. Very easy to understand
  - 2. Fairly easy to understand
  - 3. Easy
  - 4. Fairly difficult to understand
  - 5. Very difficult to understand
- 2. How easy or difficult was it to open the test cassette package?
  - 1. Very easy
  - **2.** Fairly easy
  - 3. Easy
  - 4. Fairly difficult
  - 5. Very difficult
- **3.** How easy or difficult was it to remove the sealed film covering from the sample collection tube?
  - 1. Very easy
  - 2. Fairly easy
  - 3. Easy
  - 4. Fairly difficult
  - 5. Very difficult

- **4.** How easy or difficult was it to understand the instructions on how to collect the sample from your nose or from another person?
  - **1.** Very easy to understand
  - 2. Fairly easy to understand
  - 3. Easy
  - 4. Fairly difficult to understand
  - 5. Very difficult to understand
- 5. How easy or difficult was it to understand the instructions to swirl the swab in the collection tube?
  - 1. Very easy to understand
  - 2. Fairly easy to understand
  - 3. Easy
  - 4. Fairly difficult to understand
  - 5. Very difficult to understand
- 6. How easy or difficult was it to understand the instructions on how to lift the swab out of the liquid and squeeze the collection tube?
  - 1. Very easy
  - 2. Fairly easy
  - 3. Easy
  - 4. Fairly difficult
  - 5. Very difficult

- 7. How easy or difficult was it to insert the nozzle lid onto the sample collection tube?
  - 1. Very easy
  - 2. Fairly easy
  - 3. Easy
  - 4. Fairly difficult
  - 5. Very difficult
- **8.** How easy or difficult was it to understand the instructions to add the sample from the collection tube to the sample well of the test cassette?
  - **1.** Very easy to understand
  - 2. Fairly easy to understand
  - 3. Easy
  - 4. Fairly difficult to understand
  - 5. Very difficult to understand
- 9. How easy or difficult was it to add the 3 drops into the test cassette?
  - 1. Very easy
  - 2. Fairly easy
  - 3. Easy
  - **4.** Fairly difficult
  - 5. Very difficult

10. How easy or difficult was it to read the test results?

- 1. Very easy
- 2. Fairly easy
- 3. Easy
- 4. Fairly difficult
- 5. Very difficult

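### Section 5.2 ties study-relatedness to nasal swab collection alone, so an adverse event caused by the kit's liquid, tube, nozzle or cassette would be reported but not attributed to the study

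*Combined protocol and SAP*

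**What the plan says.** Section 5.2 makes three statements that bear on this point.

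- **Onset.** An adverse event is an untoward medical event "with onset after the first study-specific procedure", and it counts whether or not it is thought to be related.
- **Reporting.** Every adverse event that is observed or reported goes to the sponsor within 24 hours, again regardless of relatedness.
- **Relatedness.** An event is study-related if it "follows a reasonable temporal sequence from a study related procedure and could readily have been produced by that study procedure". The next sentence narrows this: "For the purpose of this study, only the collection of nasal nares swab is considered to be the study procedure".

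Sections 1.3.1 and 5.4 take a similar line. Both name swab collection as the one study-related procedure that could affect subject safety.

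The test procedure is much wider. Section 3.1 lists the contents of each box as a swab, a cassette and a collection tube with nozzle lid. Section 3.5 has the subject collect the sample, run the test and read it. Its critical steps include, for example, "Lift the swab out of the liquid in the collection tube and squeeze the tube against the swab tip 3 times". The questionnaire in section 11 adds handling that 3.5 does not list, such as opening the cassette package and, in question 3, "How easy or difficult was it to remove the sealed film covering from the sample collection tube".

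**The concern.** The investigational product is the whole kit, and it is used by people without medical or laboratory training. The synopsis requires at least 30 completed subjects, of whom at least 15 test a child aged 2 to 13. If a user spills or splashes the tube liquid while squeezing the tube or fitting the nozzle, swab collection did not produce that event. Under 5.2 it therefore fails the only stated test of relatedness.

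What is at stake is attribution. Section 7.1 treats the study as part of risk mitigation for user errors and uses the observations to revise the Quick Reference Instructions (QRI). Harm from mishandling the tube or nozzle is a use error of direct interest there. A rule that labels it unrelated to the study works against that aim. It also means that the statements in 1.3.1 and 5.4, that only the swab matters for safety, could not be contradicted by any event coded as related.

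**Working it through.** The plan gives no figure to reproduce. The check is a count of steps, followed by a reading of the definitions against each other.

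**Step count (section 3.5, critical steps)**

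| Step | Swab collection? | Tube or its liquid? |
|---|---|---|
| 1. Swab each nostril | Yes | No |
| 2. Rotate swab in the liquid | No | Yes |
| 3. Lift swab, squeeze tube against it | No | Yes |
| 4. Squeeze tube while taking swab out | No | Yes |
| 5. Press on the nozzle lid | No | Yes |
| 6. Transfer 3 drops to the cassette | No | Yes |
| 7. Leave the cassette in place | No | No |
| 8. Read at 15 to 20 minutes | No | No |

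Steps outside swab collection: 8 − 1 = 7. Of these, steps involving the tube or its liquid: 7 − 2 = 5.

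**Relatedness**

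1. To be related, an event must be one that the study procedure could readily have produced (5.2).
2. The study procedure is swab collection only (5.2).
3. Harm during steps 2 to 6 that comes from the liquid, tube, nozzle or cassette is not something swab collection could readily have produced.
4. Such an event therefore does not meet the stated test. No other section provides a device-related category or a second route to relatedness.

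**Reporting**

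Such an event after the swab is still an adverse event and still reportable within 24 hours. What is lost is the attribution, not the record.

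**Onset**

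Whether harm before the swab is an adverse event at all depends on two conditions:

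- The first study-specific procedure in the onset definition must mean the swab. Section 5.2 does not define the term separately from the study procedure. Section 8.2 speaks of study-specific procedures in the plural, and 5.4 implies that other study-related procedures exist.
- The kit must be opened before swabbing. The only support is the order of the questionnaire, where package opening and film removal (questions 2 and 3) come before sample collection (question 4). The QRI, which would fix the order, is not in the documents.

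If both hold, a spill while removing the film falls before the window. If either fails, it does not. The text does not decide between them.

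**The case against.** The strongest reply is that only a label changes. All adverse events are reported regardless of relatedness, so the sponsor would still see a splash or a swallowed drop. The swab-only position also runs through 1.3.1, 5.2 and 5.4, so it looks like a deliberate risk judgement for a single visit of about one hour. The documents give neither the composition of the liquid nor any hazard for it, so the examples are hypothetical. The step count measures steps, not risk, and steps 7 and 8 have no evident route to injury. Finally, 5.2 says an event is related *if* it meets the test, not *only if*.

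Most of this stands as a limit on size. It does not rescue the sentence. Expecting little harm from the kit is a reason to expect few such events; it is not a reason to make them unattributable when they occur. Although 5.2 says *if*, it offers no other criterion, so a site following it would naturally record the event as unrelated.

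A reader might infer three stronger points, none of which the documents support:

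- **That the safety conclusion is favourable by definition.** The plan has no safety endpoint, analysis or acceptance criterion. Its endpoints and the 7.1 criteria concern usability only.
- **That 5.1 contradicts 5.2.** The statement "All samples should be handled as potentially infectious" is a precaution on handling and disposal. It says nothing about causality and can stand beside 5.2.
- **That 6.2 removes the duty of care for kit-caused harm.** The investigator's task there is "Coordinating and providing reasonable medical care to subjects for an adverse event related to study participation". Relation to study participation is not the term defined in 5.2, and using the supplied kit is plainly participation. Section 6.2 also separately requires protection of subjects' safety and welfare.

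**Conclusion.** The point holds for attribution. Section 5.2 defines the study procedure more narrowly than the study that 3.5 describes, so an adverse event caused by the liquid, tube, nozzle or cassette would be reported but would not qualify as study-related. The definition leaves out 7 of the 8 critical steps, of which the 5 involving the tube or its liquid are those where harm is most plausible. The rule applies to all of the 30 or more subjects.

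The practical effect is modest: no endpoint, analysis or success criterion changes, and reporting of events after the swab is intact. The documents give no event rate, so the number of events affected cannot be estimated.

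The conclusion assumes that sites apply 5.2 as written and that the adverse event form, which is not in the documents, has no separate field for device causality. It would be going too far to state as fact that harm before the swab is not an adverse event. That is one possible reading, which the wording leaves open and should close.

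**What to change.** In 5.2, replace the swab-only sentence with wording such as: *For this study, the study procedure is any handling or use of the test kit, from opening the box to disposal of its components, including nasal swab collection.* State in the same section that adverse event onset runs from the moment the kit is handed to the user, which settles the onset question whatever order the QRI prescribes. Align the statements in 1.3.1 and 5.4 that present swab collection as the only study-related procedure with a safety impact, and match the adverse event form.

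The cost is wording in three sections and one form, plus the IRB review that 8.1 requires for any amendment. No extra subjects, visits or staff are needed. The downside is that a few more events may be classed as related.
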